Research process	
Each subject received a 6-month treatment of 1 bag of amino acid peritoneal dialysis and 2-4 bags of glucose peritoneal dialysis fluid per day (the amount of glucose peritoneal dialysis fluid was determined according to the treatment protocol at screening when the patient entered the study). Before and during treatment, in the 1st, 3rd and 6th months, the subjects were evaluated for various efficacy and safety indicators
 
Estimate and record any adverse events or serious adverse events. Follow up monthly during treatment assess subjective feelings (infusion pain, abdominal distension), blood pressure, weight, urine volume, and ultrafiltration.

Endpoint of efficacy	Efficacy indicators: serum albumin, prealbumin and body mass, body mass index (Body mass index, BMI), lean body mass index (con icity index, CI), waist circumference and grip strength, upper arm muscle circumference, standardized protein catabolic rate (Normalized protein catabolic rate, nPCR), standardized protein total nitrogen excretion rate (Normalized protein nitrogen appearance,nPNA). Glycated hemoglobin, fasting blood glucose, Nt-pro BNP, weekly urea clearance index (Kt/V), weekly creatinine clearance (Ccr), and oral glucose tolerance test (peritoneal equilibration test, PET)
Security assessment	Safety indicators: patient blood pressure, ultrafiltration volume, urine volume, Nt-pro BNP, Kt/V, Ccr, PET, adverse event monitoring.

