4.1 Research phase and process

This study plans to enroll 140 patients with maintenance peritoneal dialysis who meet the inclusion and exclusion criteria, and is expected to be conducted in 5 centers. The study period for each subject is 6 months, and the entire study project will be completed in about 1 year. The study was divided into two phases: screening and treatment.

Screening period: Within 1 month before enrollment, patients who meet the inclusion criteria are initially screened, including physical examination, blood pressure

measurement, body weight measurement, BMI calculation, CI calculation, skinfold thickness measurement, waist circumference and grip strength measurement, upper arm muscle circumference measurement, SGA score, urine volume, ultrafiltration volume, biochemical and liver and kidney function tests, serum albumin, prealbumin, nPCR, nPNA, Kt/V and Ccr, Nt-pro BNP, hepatitis B related antigen and antibody, hepatitis C antibodies, HIV antibodies and other indicators were measured, and subjective nutritional score (SGA) and PET tests were performed. At the same time, explain the purpose, method, benefits and risks of this study to the patient and obtain his/her written informed consent. At the same time, inform the patient

The patient introduces the specific protocol and precautions of this study.

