The daily use of 1 bag of amino acid peritoneal dialysis fluid is during the nighttime sleep period, while the daily use of 2-4 bags of glucose peritoneal dialysis fluid is during the daytime. The total daily infusion volume, each infusion volume, dwell time, and each excretion volume for each subject are adjusted by the researcher based on individual patient conditions and standardized prescriptions. During treatment, subjects should follow the researcher's guidance for daily life and dietary management, and regularly visit the research center for follow-up and examinations. In the third and sixth months of treatment, subjects should repeat the screening period

All evaluation items and any adverse events or serious adverse events are recorded.

The research process is shown in Table 1:

Table 1: Research process table

Evaluate projects	Screening period/baseline	stage of therapy					
		1 month	2 months	3 months	4 months	5 months	6 months
informed consent	√	×	×	×	×	×	×
Inclusion and exclusion criteria	√	×	×	×	×	×	×
Collect demographic data	√	×	×	×	×	×	×
Symptoms (loss of appetite, nausea, vomiting, abdominal distension, Infusion pain, edema, etc.)	√	√	√	√	√	√	√

Previous illness/treatment	✓	✗	✗	✗	✗	✗	✗
Combination therapy with concomitant medication	✓	✓	✓	✓	✓	✓	✓
allergic history	✓	✗	✗	✗	✗	✗	✗
SGA	✓	✓	✓	✓	✓	✓	✓
check-up	✓	✓	✓	✓	✓	✓	✓
vital sign	✓	✓	✓	✓	✓	✓	✓
Ultrafiltration volume	✓	✓	✓	✓	✓	✓	✓
UPD	✓	✓	✓	✓	✓	✓	✓
BMI	✓	✓	✓	✓	✓	✓	✓
CI	✓	✗	✗	✓	✗	✗	✓
skin-fold thickness	✓	✗	✗	✓	✗	✗	✓
Waist circumference and grip strength, upper arm muscle circumference	✓	✗	✗	✓	✗	✗	✓
Hepatitis B related antigen antibody, hepatitis C antibody, HIV antibody	✓	✗	✗	✗	✗	✗	✗
Biochemistry and liver and kidney function (including serum albumin, Prealbumin), glycosylated hemoglobin	✓	✗	✗	✓	✗	✗	✓
White, fasting blood sugar							
Nt-Pro BNP	✓	✗	✗	✓	✗	✗	✓
nPCR	✓	✗	✗	✓	✗	✗	✓

nPNA	✓	✗	✗	✓	✗	✗	✓
Kt/V and Ccr	✓	✗	✗	✓	✗	✗	✓
PET	✓	✗	✗	✓	✗	✗	✓
adverse event	✓	✓	✓	✓	✓	✓	✓

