(16) Conduct PET testing: After subjects are enrolled in this study, regular PET tests should be conducted to evaluate their peritoneal dialysis material transport characteristics. The PET testing method follows the standard PET (Standard PET) proposed by Twardowski. Measure the glucose concentration in the effluent and compare it with that in the infused fluid to calculate the D/P ratio and the D/D0 ratio. Based on the D/P ratio and the D/D0 ratio, subjects are categorized into four types: high transport, high average transport, low average transport, and low transport. The results of the PET testing should be

recorded in the CRF, noting any abnormalities or differences common associated clinical manifestations.

(17) Adverse events: The recording time is from the start of treatment to the end of survival follow-up, and only AE related to this study is collected, Including adverse events of special concern.

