4.2.2 During treatment

During the treatment period, each participant received a regimen of 1 bag of amino acid peritoneal dialysis and 2-4 bags of glucose peritoneal dialysis fluid daily for 6 months (the amount of glucose peritoneal dialysis fluid was determined based on the treatment plan at the time of screening when the patient entered the study). In the third and sixth months of the treatment period, participants should repeat all assessments from the screening phase and record any adverse events or serious adverse events. Monthly follow-up evaluations were conducted during the treatment period. Observe (infusion pain, abdominal distension), blood pressure, weight, urine volume, ultrafiltration.

5. Treatment plan

The treatment protocol of this study is as follows:

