6.1 Definition of adverse events

Adverse events (Adverse Event, AE) are any harmful medical events that occur during a clinical trial. Events, regardless of whether they have a causal relationship with the test drug. Adverse events include the following: Adverse reactions related to the test drug (Adverse Reaction, AR): refers to the normal use conditions. Any harmful medical event caused by the pharmacological action of the test drug or for other reasons. Adverse events not related to the test drug: any harmful medical event that occurs during a clinical

trial, However, it was scientifically determined that there was no causal relationship with the test drug.

Serious adverse events (Serious Adverse Event, SAE): refers to those that occur during clinical trials

Any harmful medical event, regardless of whether it has a causal relationship with the investigational drug, that results in one of the following outcomes:

Causing death;

Life-threatening (i.e., potentially fatal if not promptly intervened);

Hospitalization or extension of hospitalization is required;

Causing permanent or significant disability or impairment;

Causing congenital malformations or birth defects;

Major medical intervention (such as surgery, blood transfusion, etc.) is required.

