6.2 Observation and handling of adverse events

In this study, all subjects should undergo regular safety assessments, including subjective patient reports (such as abdominal pain, bloating), blood pressure, ultrafiltration volume, urine output, Nt-pro BNP, Kt/V, Ccr, PET, and other indicators. Researchers should document all adverse events that occur during the clinical trial and observe and manage them. The principles of inspection and handling are as follows:

The investigator should ask the subject if he or she feels any discomfort and actively observe whether the subject has any abnormal symptoms present.

Researchers should record the name, time of occurrence, duration, severity, and trial of all adverse events information such as causality, treatment measures and outcomes of the drug should be filled in the adverse event report form.

Researchers should provide appropriate treatment and support measures according to the nature and severity of adverse events closely monitor the subject's condition.

Researchers should decide whether to continue use based on the causal relationship and impact of adverse events and trial drugs. The test drug or withdrawal from the study.

Researchers should report all adverse events that occur during clinical trials to the ethics committee and sponsor in a timely manner events and track and update them as required.

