6.3 Criteria for judging the relationship between adverse events and tests

The causal relationship between adverse events and the test drug should be judged according to the following criteria:

Assured of relevance (Definitely Related): Adverse events are related to the pharmacological action of the investigational drug or a known adverse event

The results were consistent and other possible causes were ruled out.

Most likely related (Probably Related): Adverse event and pharmacological action of the investigational drug or known no The good response is consistent and other possible causes are unlikely.

May be related (Possibly Related): Adverse event is related to the pharmacological action of the investigational drug or a known adverse eventThere are some similarities in the reaction, but there are other possible reasons.

It is unlikely to be related (Unlikely Related): the adverse event is related to the pharmacological action of the investigational drug or is known. There was no clear similarity in the adverse reactions and there were other more likely causes.

Irrelevant (Not Related): The adverse event is completely unrelated to the pharmacological action of the test drug or a known adverse reaction. It does not match and there are other clear reasons.

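### Section 4.1 item (17) limits collection to study-related adverse events, up to a follow-up phase the study does not have, while other sections require all adverse events

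*Combined protocol and SAP*

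**What the plan says.** Item (17) in the list of assessments in section 4.1 sets both the scope and the window of safety data collection: "The recording time is from the start of treatment to the end of survival follow-up, and only AE related to this study is collected". It adds that events of special concern are included, but no section defines these.

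Elsewhere the plan is broader:

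- The synopsis (research process) asks staff to "Estimate and record any adverse events or serious adverse events".
- Section 4.1, before Table 1, says of months 3 and 6: "All evaluation items and any adverse events or serious adverse events are recorded".
- Section 4.2.2 says "participants should repeat all assessments from the screening phase and record any adverse events or serious adverse events".
- Section 6.1 defines adverse events as harmful medical "Events, regardless of whether they have a causal relationship with the test drug".
- Section 6.2 says "Researchers should document all adverse events that occur during the clinical trial".
- Section 6.5 requires every adverse event to go on the report form within 24 hours. It also gives a reporting route for serious unexpected reactions unrelated to the test drug.
- Section 7.6.4 summarises all adverse events in the safety set, and then separately by relationship to the drug.

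On timing, section 4.1 states: "The study was divided into two phases: screening and treatment". Each subject is studied for 6 months.

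**The concern.** A rule that collects only related events cannot stand beside rules that document, report and analyse all of them. The qualifier in item (17) is also undefined: it speaks of relationship to the study, whereas section 6.3 grades relationship to the test drug.

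The risk lies mainly in the analysed data. Sections 6.2 and 6.5 should ensure that unrelated events exist on report forms. But section 10.1 builds the CRF from the protocol's observation items and time points, and item (17) is the descriptive entry for adverse events in that list. Section 10.2 builds the database from the CRF. Section 9.2 lists the adverse event report form as a document separate from the CRF, and no section describes reconciling the two. A CRF faithful to item (17) could therefore leave unrelated events out of the analysis without breaching that item.

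The study is open and has no control group, so relatedness is an unblinded judgement made across five expected centres. Events filtered out at collection cannot be recovered from the database at analysis. If centres read the rule differently, their event rates would differ for that reason alone.

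**Working it through.** This is a comparison of texts. It involves no error rate, power or sample size.

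**Scope.** One clause, item (17), restricts collection. Seven places cover any or all adverse events: the synopsis and sections 4.1, 4.2.2, 6.1, 6.2, 6.5 and 7.6.4. These are not seven independent rules. The first three repeat essentially one instruction, 6.1 is a definition, and 7.6.4 is an analysis rule. Sections 6.2 and 6.5 are the separate documentation and reporting rules, and both say all.

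**Causality grades.** Section 6.3 has five: Definitely, Probably, Possibly, Unlikely and Not Related. The last reads: "Irrelevant (Not Related): The adverse event is completely unrelated to the pharmacological action of the test drug or a known adverse reaction". If item (17) is read as drug causality:

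- dropping Not Related alone removes 1 of 5 grades;
- dropping Unlikely Related as well removes 2 of 5.

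These are counts of categories, not of events. The lower categories would be largely empty, so the breakdown by drug relationship in section 7.6.4 could not be produced in full. Tables restricted to related events could still be produced.

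**Window.** Item (17) starts recording at the start of treatment and ends it after a survival follow-up.

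- End: the plan has two phases and 6 months per subject, Table 1 stops at month 6, and the work schedule (Table 2) lists only treatment and follow-up of subjects. No survival follow-up appears anywhere else.
- Start: Table 1 ticks adverse events at screening/baseline and at months 1 to 6, which is 1 + 6 = 7 ticks. One of the 7, the screening tick, falls before item (17)'s window opens.

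**Precedence.** No section ranks these rules. Section 9.2 comes closest, but it first asks researchers to record events related to the study and then to report any adverse event, so it does not settle the matter.

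**Size.** The documents give no adverse event rates, so the number of events that could be lost cannot be derived.

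**The case against.** The strongest reply is that the dedicated safety chapter already governs collection. Section 6.2 requires all events to be documented with causality, section 6.5 sets deadlines for all events and for serious ones, and section 7.6.4 analyses all of them. Section 10.1 describes the CRF as holding all of a subject's data and lists adverse event records among its contents. Table 1 has an unrestricted adverse event row. Sections 8.4 and 10.2 call for checks on completeness and consistency. On this view, what remains is a possible transfer gap and not a demonstrated loss.

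The text also reads like a translation, and the restriction may have been meant as events occurring in the study. Finally, safety is a secondary objective analysed descriptively in a post-marketing study, and no primary test is affected.

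Much of this is fair. Loss of events is conditional on a centre or the CRF following item (17), and the primary analysis is untouched. But the contradiction remains. Listing adverse event records as CRF content does not say which events belong there, and the quality checks are generic. A possible translation slip does not cancel the word only in the text that centres will read. Item (17) is also the one place that gives an explicit start and end for recording, so centres cannot simply ignore it.

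**Conclusion.** The concern holds, and the text must be fixed. As written, the plan sets incompatible rules for which adverse events are collected and ends recording at a phase that does not exist, with nothing to say which rule prevails. One clause stands against seven places, of which sections 6.2 and 6.5 are the separate documentation and reporting rules. Item (17) would exclude one or two of the five causality grades, and one of the seven adverse event ticks in Table 1 lies outside its window.

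The grade counts assume that relationship to the study means relationship to the test drug. The consequence for the analysis assumes that the CRF or at least one centre follows item (17). In that case the summary of all adverse events would be incomplete. How incomplete cannot be estimated from the documents.

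**What to change.** Reword item (17) so that every adverse event is recorded regardless of relationship and graded by section 6.3. Delete the restriction to study-related events and the reference to survival follow-up. State one recording window ending at the month-6 or termination visit, and bring the screening tick in Table 1 and the CRF into line with it. The cut-off would apply to new events and would not prevent the tracking of ongoing ones that section 6.2 requires. Add one line stating that the report forms under section 6.5 are reconciled with the CRF adverse event records before analysis.

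The cost is rewording one item, aligning the CRF, and a little more data entry at monthly visits that already cover adverse events.

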4.2 Data collection

4.2.1 Screening period

During the screening period, the following observations were performed on patients who met the inclusion criteria:

Informed consent: Explain the purpose, method, benefits and risks of this study to the patient, and obtain his/her written informed consent.

Inclusion/exclusion criteria: Check whether the patient meets the inclusion and exclusion criteria.

Past history/comorbidities/treatment: Record the patient's past history, comorbidities and treatment.

Comprehensive Subjective Nutritional Assessment (SGA): Using the improved method of SGA assessment in the 2010 version of The Standard Operating Procedures for Peritoneal Dialysis, patients were comprehensively assessed for nutritional status, including weight change, appetite change, gastrointestinal symptoms, activity ability and complications, physical examination, etc., and patients were divided according to the scoring results. There are three categories: normal nutrition (A), mild malnutrition (B) or severe malnutrition (C).Physical examination: Measure the patient's height, weight, blood pressure, heart rate, respiratory rate and other indicators, and calculate

BMI (BMI= body mass / height² (kg/m²)).

Blood pressure measurement: Use standardized methods and equipment to measure the patient's systolic and diastolic blood pressure and record itaverage value.

Body weight measurement: Use an electronic scale to measure the dry weight of the patient and record the value.

BMI Calculation: Calculate the patient's BMI based on weight and height data, and record its value.

CI calculation: Use the tape measure to measure the patient's waist circumference, and calculate the patient's CI value ($CI = \text{waist circumference (m)} / \{0.109 \times [\text{body weight (kg)} / \text{height (m)}]^{1/2}\}$) according to the weight and height data, and record it numeric value.

Waist circumference and grip strength measurement: Use a tape measure to measure the patient's waist circumference and record its value. Use a grip strength gauge, according to the standard method, the grip strength of each patient's left and right hands was measured once and the average value was recorded.

Triceps skinfold thickness measurement: Use a skinfold thickness gauge and follow a standardized method on the right side of the patient the triceps, the thickness of the skin fold was measured and recorded.

Arm muscle circumference measurement: Use a tape measure to measure the circumference of the patient's right arm, and calculate the patient's upper arm muscle circumference ($= \text{arm circumference (cm)} 0.3142 \times \text{triceps skinfold thickness (mm)}$) according to the data of skinfold thickness, and record it the values.

Biochemical and liver and kidney function tests: venous blood samples were collected from patients, and serum creatinine, blood urea nitrogen, potassium, sodium, calcium, phosphorus, magnesium, bicarbonate, total protein, albumin, globule were measured by automatic biochemical analyzer

Indicators such as white, bilirubin, alanine transaminase, aspartate transaminase and alkaline phosphatase were measured and their values were recorded.

Serum albumin, prealbumin: venous blood samples were collected from patients and bromophenol green method and immunoturbidimetric method were used,

The serum albumin and prealbumin levels of patients were measured separately and their values were recorded.

Indicators such as nPCR,nPNA, Kt/V and Ccr were measured: according to the 2010 version of the Standard Operating Procedure for Peritoneal Dialysis, the protein catabolic rate nPCR (g/(kg · d)) and total protein nitrogen presentation rate of patients were calculated nPNA (g/(kg · d))、 Kt/V 、 Ccr (L/1.73 m²)。

Nt-pro BNP: According to the level of Nt-pro BNP, patients with Nt-pro BNP <11000pg/mL did not think there was heart failure or other factors affecting the level of Nt -pro BNP; patients with Nt-pro BNP ≥ 11000 pg/mL did not think there was heart failure or other factors affecting the level of Nt-pro BNP

The study process was closely monitored for possible factors such as heart failure or other factors affecting Nt-pro BNP levels.

Volume of urine, ultrafiltration: based on the patient's recent 1-month home monitoring records, record the average daily value.

PET test: Using standardized methods, patients were subjected to a peritoneal balance test (PET), which included the infusion of 2L of 2.5% glucose peritoneal dialysis fluid for 2 hours, followed by a 4-hour stay to measure creatinine and glucose concentrations. The infused fluid and the excreted fluid were then measured for weight, osmotic pressure, protein content, and creatinine content. Based on the results, the patient's ultrafiltration volume, urea nitrogen clearance rate, creatinine clearance rate, D/P creatinine ratio, and D/D0 creatinine were calculated

The ratio, D/P urea nitrogen ratio, D/D0 urea nitrogen ratio and other indexes were used to classify patients into high transport type (H)

There are four types: high average transport type (HA), low average transport type (LA) or low transport type (L).

4.2.2 During treatment

During the treatment period, each participant received a regimen of 1 bag of amino acid peritoneal dialysis and 2-4 bags of glucose peritoneal dialysis fluid daily for 6 months (the amount of glucose peritoneal dialysis fluid was determined based on the treatment plan at the time of screening when the patient entered the study). In the third and sixth months of the treatment period, participants should repeat all assessments from the screening phase and record any adverse events or serious adverse events. Monthly follow-up evaluations were conducted during the treatment period. Observe (infusion pain, abdominal distension), blood pressure, weight, urine volume, ultrafiltration.

5. Treatment plan

The treatment protocol of this study is as follows:

